However, due to the only recent identification of this process, there has not yet been an attempt to stimulate the pharyngeal muscles with noradrenergic drugs in sleeping humans. Now, more than ever, the stage has been set for stimulating the pharyngeal muscles across both NREM and REM sleep.

II. SPECIFIC AIMS

To determine the effect of noradrenergic and antimuscarinic on genioglossus activity and OSA severity. We hypothesize that existing drugs with these neurotransmitter profiles could (partially) restore pharyngeal muscle activity in humans during sleep.

Specifically, we will test this hypothesis by assessing;

1. The effect of pseudoephedrine (an α 1-adrenergic agonist) combined with diphenhydramine (an antihistaminic with sedative properties and with antimuscarinic action) on EMG_{GG} during sleep (PART D).

III. SUBJECT SELECTION

We will recruit a group of subjects with OSA. These subjects will be recruited from the community and be between 21-65 years old. The purpose of studying patients with OSA is to determine what effect this drugs will have on improving the patient's OSA severity.

a) Obstructive Sleep Apnea Patients (n= 15): Patients with OSA will be recruited from our clinical sleep laboratory at Brigham and Women's Hospital, as well as from our existing database of OSA patients. These individuals will be otherwise healthy (except for well-controlled hypertension; defined as systolic blood pressure <140 mmHg and diastolic <90 mmHg) with no active medical problems and on no medication that could affect respiration or muscle control. All will be 21-65 years of age. Both men and women will have an apnea-hypopnea index (AHI) >15 events/hr during supine NREM sleep. These individuals will be recruited to encompass a large range of AHI's (from 10 to >60/hour).

b) Exclusion criteria:

- Any active medical condition other than well controlled hypertension, hyperlipidemia, gastroesophageal reflux disease, depression.
- Any medication known to influence breathing, sleep/arousal or muscle physiology.
- Claustrophobia.
- Inability to sleep supine.
- Allergy to lidocaine, Oxymetazoline HCl, pseudoephedrine HCl, diphenhydramine.
- Individuals with underlying cardiac disease, such as arrhythmias.
- History of seizures
- History of moderate or severe renal impairment
- For women: Pregnancy.

We will consider all applicants regardless of sex, race, color, creed, or national origin.

DETAILED PROTOCOL

Version: October 17, 2016

IV. SUBJECT ENROLLMENT

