Two overnight sleep studies will be performed approximately 1 week apart: a placebo night and a pseudoephedrine-plus-diphenhydramine (120+50mg PO, DAW1033D) night, in double-blinded randomized control design. For each night, the subjects will arrive at the sleep laboratory at approximately 7:00pm. A physician will complete a complete physical and medical history. The placebo or DAW1033D will be administered 30 minutes before lights out. At least 15 minutes of quiet wakefulness will be recorded to quantify the subject's awake EMG_{GG} activity. Subjects will then be allowed to fall asleep during which we will assess EMG_{GG} activity throughout the rest of the evening (see below for details).

Measurements and equipment:

Subjects will be instrumented with standard polysomnography (PSG) recording sensors. Sleep stage and arousals will be measured with electrodes pasted on to the scalp, face, chin and chest (EEG, EOG, EKG,

DETAILED PROTOCOL

Version: October 17, 2016

chin EMG). Paste-on EMG electrodes will be placed over the anterior tibialis muscle to detect leg movements. Respiratory effort belts will be placed around the chest and abdomen to measure breathing movements. Oxygen saturation will be measured continuously with a pulse oximetry probe placed on either the fingertip or earlobe. Snoring will be detected with a small microphone positioned over the suprasternal notch. Body position will be recorded with a sensor taped to the thoracic belt. Each of these devices is standard for diagnostic PSG and should not be uncomfortable.

One nostril and the back of the throat will be anesthetized with 4% lidocaine; only 2–3 ml (80–120 mg) of lidocaine is used. One small, flexible pressure-tipped catheter (Millar) will then be inserted through the anesthetized nostril until the tip of the catheter is located just above the epiglottis (or in the esophagus) by visual inspection through the mouth; the catheter is then taped to the nose to prevent movement. This catheter is used to assess upper airway negative pressure and to calculate airflow resistance both awake and during sleep.

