Electromyogram activity from the genioglossus (EMG_{GG}) muscle (a major upper airway dilator muscle) may also be recorded using unipolar intramuscular electrodes as described in our previous studies (1, 23, 24). Two 25 gauge needles containing 30 gauge, Teflon-coated stainless steel wires are inserted into the muscle after topical anaesthesia with 4% lidocaine. A maximum of 2 mls of lidocaine will be used for needle insertion. If the patient cannot tolerate needle insertion once the maximum dose of lidocaine has been applied, then the procedure will be stopped. The needle is immediately removed leaving the wire in place. Both electrodes are referenced to a single ground producing a bipolar recording. GG needle placement is as follows: The muscle is approached through the floor of the mouth with each needle being inserted about 3-5 mm lateral to the frenulum and about 12-15 mm into the body of the genioglossus near its insertion into the mandible. Once the electrodes are placed, the EMG signal is amplified, rectified, and integrated on a moving time average basis with a time constant of 100 msec (CWE Incorporated).

The subject is then asked to lay down (supine) and a comfortable sealed mask will be placed over the nose and held in place with straps. The mask allows monitoring of breathing (inspiratory flow by pneumotachograph which can be integrated to tidal volume) and expired carbon dioxide levels (PCO₂) using a calibrated infrared CO₂ analyzer (Capnograph/Oximeter Monitor), and if available, end-tidal oxygen levels using a calibrated O₂ analyzer.

Tests performed during wakefulness.

The patients, with the described monitoring equipment in place, will undertake two tests before going to sleep for the night, although some of the testing may not be performed in all subjects depending on availability of equipment, scheduling issues and willingness of the subject to undergo all of the testing.

1. Upper airway muscle activity during wakefulness

The subject will be asked to perform several maneuvers to assess the activity of the GG during wakefulness. The maneuvers include a maximal tongue protrusion, inspiration against a closed airway, swallow and maximum voluntary ventilation. Each of these maneuvers will be repeated 3 times.

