Muscle activity will be quantified using standard procedures described in our previous studies (1, 23, 24). Briefly, the raw EMG_{GG} signal will be rectified and smoothed with a 100 msec window. The peak phasic, as well as tonic, activity of the smoothed signal will be identified for each breath. Data from quiet wakefulness (free of swallowing and movement artifacts) will be averaged to determine the peak phasic and tonic activities during this state. The same will be done for stable NREM and REM sleep (free of arousals and other artifacts). Both NREM and REM sleep will be analyzed, recognizing that REM is less frequent on these drugs. Pharyngeal muscle responsiveness will be determined by calculating the slope and intercept of the epiglottic pressure versus muscle EMG relationship.

Reimbursement

Subjects will receive \$100/night for participation in each overnight study (TOTAL = \$200 for each PART of the study). Reimbursement for parking expenses will be provided.

If the subjects will repeat a part or the entire protocol because of insufficient data collection, they will be reimbursed \$100 for any extra night.

VI. BIOSTATISTICAL ANALYSIS

Subjects will be prospectively enrolled until 10 had completed both study nights. Sample size was chosen to facilitate detection of a clinically-important $50 \pm 50\%$ reduction in AHI. Calculations were based on previous studies conducted in our laboratory. To account for a ~30% failure rate approximately 13 patients will be enrolled in the study.

In order to reduce the influence of potential outlier, data will be expressed as median [interquartile range] and data on placebo vs DAW1033D will be compared using Wilcoxon test. A p value < 0.05 will be considered as statistically significant.

In the pilot study using the noradrenergic drug desipramine, the average difference in EMG_{GG} activity (between the placebo night and the drug night, with EMG_{GG} quantified as a percentage of wakefulness) was $47 \pm 20\%$. In order to detect this difference with 80% power and a 5% level of significance, 6 subjects would need to be studied.

DETAILED PROTOCOL

Version: October 17, 2016

VII. RISKS AND DISCOMFORTS

We believe that the risks associated with participation in this study are minimal. All study procedures have been conducted in our laboratory without serious incident. Anticipated risks and discomforts are listed below:

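### No primary outcome is named and one p < 0.05 rule covers every comparison, so the false-positive rate exceeds 5%: about 10% for the two sized outcomes, more if all described measures are tested

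*Combined protocol and SAP*

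**What the plan says.** Section II states a joint aim without ranking its two parts: "To determine the effect of noradrenergic and antimuscarinic on genioglossus activity and OSA severity". The one numbered aim beneath it concerns only genioglossus EMG (EMG_GG) during sleep.

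Section VI starts from the other outcome. For AHI it says "Sample size was chosen to facilitate detection of a clinically-important" reduction of 50 ± 50%, with enrolment continuing until 10 subjects have completed both nights. It then gives a second calculation for EMG_GG as a percentage of wakefulness: a difference of 47 ± 20%, 80% power, 5% significance, 6 subjects.

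The analysis rule is general: "data on placebo vs DAW1033D will be compared using Wilcoxon test", followed by "A p value < 0.05 will be considered as statistically significant". Neither sentence is tied to a particular outcome, and no multiplicity adjustment is given.

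The Data Analysis part of Section V describes peak phasic and tonic EMG_GG, analysed in both NREM and REM sleep, and muscle responsiveness obtained by "calculating the slope and intercept of the epiglottic pressure versus muscle EMG relationship". It does not mention AHI. Under Measurements and equipment, EMG_GG "may also be recorded using unipolar intramuscular electrodes", so it is not certain to be available in every subject.

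**The concern.** The places from which a reader might infer the primary outcome point in different directions. The numbered aim points to EMG_GG, while the enrolment target points to AHI. AHI is missing from the description of derived measures, and EMG_GG is optional in the description of measurements. Neither can safely be taken as the implicit primary.

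With one significance threshold for everything and no order of testing, the choice of headline result stays open until the data are seen. Whichever outcome crosses 0.05 could then be presented as the finding, and that statement would not carry the 5% error rate the threshold implies. With about 10 completers there is little further evidence in the study against which to check a chance result.

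**Working it through.** **Inputs.** Threshold 0.05 (Section VI), taken as two-sided because the sidedness is not stated. Wilcoxon test (Section VI), taken as the signed-rank test because each subject has both nights: "Two overnight sleep studies will be performed approximately 1 week apart: a placebo night" and a drug night (Section V). AHI effect 50 with SD 50 and 10 completers; EMG_GG effect 47 with SD 20 and 6 subjects (Section VI).

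**1. The plan's own sample sizes.**
- AHI: standardized effect 50/50 = 1.0. A paired t-test with n = 10 has noncentrality √10 = 3.16 and critical value 2.262, giving 80.3% power. The stated 10 is reproduced if 80% power was intended; Section VI gives no power for AHI. Simulated signed-rank power at n = 10 is about 79%.
- EMG_GG: standardized effect 47/20 = 2.35. A paired t-test reaches 86.5% power at n = 4, so the stated 6 is sufficient. Six is also the smallest n at which a two-sided signed-rank test can reach p < 0.05 (minimum p = 2/2^6 = 0.031).

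Both calculations therefore stand as separate single-outcome calculations. Nothing in them ranks one outcome above the other.

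**2. Counting the comparisons.** AHI (1), phasic and tonic EMG_GG in NREM and REM (2 × 2 = 4), slope and intercept (2): 1 + 4 + 2 = 7. The minimum reading is the two outcomes that Section VI sizes.

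**3. Chance of at least one false positive when the drug has no effect, tests independent: 1 − 0.95^k.**

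| Tests (k) | Calculation | Result |
|---|---|---|
| 2 (AHI, one EMG_GG measure) | 1 − 0.9025 | 9.8% |
| 5 (seven without the two REM measures) | 1 − 0.7738 | 22.6% |
| 7 (all described) | 1 − 0.6983 | 30.2% |

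The bound for seven tests under any dependence is 7 × 0.05 = 35%.

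**4. Allowing for correlation (k = 7, assumed equal correlations).** The documents give no correlations, so a range is shown.

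| Correlation | Normal outcomes, numerical integration | Signed-rank test, n = 10, simulated |
|---|---|---|
| 0.3 | 27.1% | 27.1% |
| 0.5 | 23.0% | 24.0% |
| 0.7 | 17.8% | 19.3% |
| 0.9 | 11.4% | 12.6% |

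**5. Allowing for the discreteness of the test and for optional EMG.** The exact two-sided signed-rank size is 4.88% at n = 10 and 3.13% at n = 6.
- All seven tests at n = 10, independent: 1 − 0.9512^7 = 29.6%.
- AHI at n = 10 and the six EMG-based measures at an assumed n = 6, independent: 1 − 0.9512 × 0.9688^6 = 1 − 0.9512 × 0.8266 = 21.4%.

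**The case against.** The strongest reply is that Section V, Data Analysis, explains how quantities are derived and does not list hypothesis tests. Section VI names only AHI and EMG_GG as a percentage of wakefulness. On that reading there are two tests and the rate is 9.8%, not 30%. This stands as a limit on the size: seven is a tally of described measures, and the plan does not commit to testing each one.

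A reader might infer that 30% is an upper limit or a realistic estimate. It is neither. It is the independence value; the bound is 35%. The EMG measures come from the same electrodes in the same subjects, and slope and intercept come from one fitted line, so positive correlation and a lower figure are plausible. Adding wakefulness EMG to enlarge the count is weak, since Section VI uses wakefulness as the denominator of the EMG outcome.

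A reader might also infer that any single p < 0.05 makes the study positive. The plan does not say so. It sets a threshold for a comparison and gives no rule for declaring overall success, and Section IX describes the study as a physiological investigation rather than a clinical trial. That lowers the stakes. It does not supply a primary outcome, and the study remains randomized, double-blind and sized against a significance threshold.

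Finally, placing AHI first puts the only numbered aim behind another outcome. That is a real cost, carried into the recommendation below.

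**Conclusion.** The concern holds in a limited form. No outcome is designated primary, the aims and the sample-size section point to different ones, and one 5% threshold covers all comparisons. The chance of at least one false positive is above 5% on any reading with two or more tests that are not perfectly correlated: 9.8% for the two sized outcomes if independent, about 30% for all seven described measures if independent, and roughly 11% to 27% for those seven at correlations of 0.9 to 0.3. Reduced EMG availability lowers it further, for example to about 21% with independent tests and EMG in six subjects.

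These figures rest on a two-sided signed-rank or equivalent test and on assumed correlations. The defect itself does not depend on the exact count. The change is worth making before unblinding, but the documents do not support describing the study as having a 30% false-positive rate.

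**What to change.** Before unblinding, add a paragraph to Section VI that does the following.

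1. Name one primary outcome, tested at two-sided 5%. AHI is the natural choice because the 10 completers were sized on it and EMG recording is optional. State the recording period, body position and sleep stage in which AHI is scored. This must be reconciled with Section V, where subjects sleep on adjusted CPAP for about 4 hours and then in the lateral position without it.
2. Name one EMG_GG measure as the key secondary outcome, for example NREM peak phasic EMG_GG as a percentage of wakefulness, tested only if the primary is significant. If the sponsor regards the numbered aim as primary, reverse the order. Either order resolves the point.
3. Report the remaining EMG measures, slope and intercept as exploratory estimates with confidence intervals and no significance claims.

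**Cost.** No extra patients are needed, and the primary keeps its power: about 80% for AHI at n = 10. A Bonferroni correction over seven tests (0.05/7 = 0.0071) would instead cut simulated signed-rank power for AHI from about 79% to about 37%. The downside is that the outcome placed second cannot be claimed on its own if the first fails. With AHI first, that happens about one time in five (1 − 0.80 = 0.20) even if the plan's 50 ± 50% assumption is correct. Defining how AHI is scored also takes more thought than a change of label.

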1. The equipment used for assessing sleep (paste on electrodes) is standard and poses no risk. The electrodes may be mildly uncomfortable and could cause some sleep interruption. Thus subjects may feel somewhat tired the day following this study.
2. Pharyngeal Pressure Catheter: Inserting the pressure catheter through the nostril and into the pharynx may be uncomfortable and could cause gagging or even vomiting. The anesthetized and fasting state substantially reduces the risk of discomfort or complications. As the subject will have a catheter in his/her pharynx and a nasal mask in place, the risk of aspiration must be considered. However, this has never been encountered after hundreds of similar studies. The catheter, once in place, does not gag the subject and the mask can easily be removed. Overall, the risk of aspiration is minimal.
 - i. Lidocaine. If the subjects have any history of lidocaine allergy, they will be excluded from the study. Excessive use of lidocaine can cause seizures, but this is reported with much higher doses than will be utilized in this study. However, subjects will be informed that lidocaine has an unpleasant taste.
3. Intramuscular EMG Determination: Needle insertion may be painful although the mucosa is topically anesthetized with lidocaine. We have found this pain to be similar to venipuncture and well tolerated. Discomfort is minimal once the needle is removed and the wire is left in place. A small amount of bleeding and/or a small bruise may occur. Both the needles and wires are sterilized. However, intramuscular or surface infection could occur, as it is impossible to sterilize the inside of the mouth. We have never encountered this problem or heard of it occurring elsewhere. There may be some residual soreness in the tongue for several hours after the wires are removed.
4. Pseudoephedrine: this drug is available at the dose of 15, 30, 60 and 120 mg as over-the-counter medication of nasal congestion and cold relief. Common side effects include arrhythmia, tachycardia, palpitations, nervousness, excitability, restlessness, dizziness, weakness, insomnia, headache, drowsiness. Other side effects may include anorexia, constipation, diarrhea, hypertension, dry throat, ischemic colitis, nausea, vomiting, xerostomia, dysuria, polyuria, urinary retention, tremor, weakness, blurred vision, diplopia, dry nose, dyspnea, nasal congestion, thickening of bronchial secretions, wheezing, tinnitus.

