5. Diphenhydramine: this drug is available at the dose of 25 and 50 mg as over-the-counter medication of allergy and cold relief. Common side effects include: sedation, sleepiness, dizziness, disturbed coordination, epigastric distress, thickening of bronchial secretions. Other side effects may include extrasystoles, hypotension, palpitations, tachycardia, blurred vision, diplopia, difficulty in micturition, urinary frequency, urinary retention, tinnitus, anorexia, constipation, diarrhea, dry mucous membranes, epigastric distress, nausea, vomiting, xerostomia.
6. Combination of pseudoephedrine and diphenhydramine: the association of these drugs is already available (at a lower dose of 60/25 mg) as over-the-counter medication for nighttime relief of allergy, sinus and cold symptoms (see for example Benadryl Allergy Sinus). The most common side effects of the combination of the drugs are constipation, diarrhea, dizziness, drowsiness, dry mouth, nose, and

DETAILED PROTOCOL

Version: October 17, 2016

throat; excitability, headache, anorexia, nausea; nervousness or anxiety, insomnia, weakness. As both drugs are commonly administered at higher doses alone, we believe that increasing the dose of the combination will not determine excessive increase in the risk of serious side effects. Furthermore, the drugs will be administered for only one night in a monitored setting: an experienced researcher will be present for the entire night checking vital signals in real time (heart rate, oxygen SaO₂, EEG), the patient will be under audio and video-surveillance. An MD will be available for the duration of the study and the following morning if necessary.

VIII. POTENTIAL BENEFITS

Although it is unlikely that there will be any direct physical benefit to the subjects from participating in this study, we will make known to each subject, if requested, some of the information we have gathered from this physiologic testing. This study provides a unique opportunity to gain insight into the specific mechanisms by which these novel drugs may improve upper airway muscle function. The results may, in the future, lead to improved strategies for the treatment of sleep apnea. However, if previously unknown abnormalities of sleep and breathing are encountered, this information will be passed onto the subject. Results can be forwarded to the primary care physician or clinician at the request of the subject.

IX. MONITORING AND QUALITY ASSURANCE

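### The supplied protocol text names no blood pressure reading after dosing, although it lists a blood pressure effect for each drug and admits patients with well-controlled hypertension

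*Combined protocol and SAP*

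**What the plan says.** **Eligibility (Section III).** Patients are to be otherwise healthy, "except for well-controlled hypertension; defined as systolic blood pressure <140 mmHg and diastolic <90 mmHg". The exclusion list repeats the allowance: "Any active medical condition other than well controlled hypertension, hyperlipidemia, gastroesophageal reflux disease, depression". The eligibility definition is the only place where the protocol treats blood pressure as a measured quantity.

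**Dose (Section V, Protocol; Section VII, item 6).** The active night is a "pseudoephedrine-plus-diphenhydramine (120+50mg PO, DAW1033D) night". Of the marketed product, item 6 says that "the association of these drugs is already available (at a lower dose of 60/25 mg").

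**Listed effects (Section VII, items 4 and 5).** For pseudoephedrine: "Other side effects may include anorexia, constipation, diarrhea, hypertension". For diphenhydramine: "Other side effects may include extrasystoles, hypotension, palpitations, tachycardia". Both sit in the lists of other, not common, side effects.

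**Risk argument (Section VII, item 6).** The protocol expects that "increasing the dose of the combination will not determine excessive increase in the risk of serious side effects". Its first reason is that each drug is commonly given alone at higher doses. It then adds that exposure is one night in a monitored setting, with a researcher present and "checking vital signals in real time (heart rate, oxygen SaO₂, EEG"), audio and video surveillance, and a physician available through the study and, if needed, the next morning.

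**The concern.** Monitoring is part of the protocol's argument for accepting the higher combined dose, but none of the three signals it names measures blood pressure. Two effects that the protocol itself lists, one in each direction, therefore have no planned means of detection after dosing. Eligibility leaves room for patients to whom a rise in pressure matters, and hypertension is the only listed side effect for which eligibility sets a numeric limit.

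A rise or fall without symptoms could pass unnoticed, and a subject could be dosed and released with no reading after the dose. There is also a reporting consequence. The adverse event definition in Section IX includes abnormal signs, so an abnormal blood pressure without symptoms could count as an event. The safety officer cannot classify what nobody measured, and a low event count would say nothing about blood pressure.

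**Working it through.** The protocol gives no figure of its own to reproduce here. The check is one ratio, followed by a walk through each study night.

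1. **Combined dose against the marketed combination.** Study dose 120 and 50 mg (Section V); marketed combination 60 and 25 mg (Section VII, item 6).
   - Pseudoephedrine: 120 / 60 = 2.0
   - Diphenhydramine: 50 / 25 = 2.0

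2. **Each component against the single-drug strengths listed.** Item 4 lists pseudoephedrine up to 120 mg; item 5 lists diphenhydramine at 25 and 50 mg.
   - Pseudoephedrine: 120 / 120 = 1.0
   - Diphenhydramine: 50 / 50 = 1.0

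   The factor of two applies to the marketed pair, not to the strengths listed for either drug alone.

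3. **Observations in the order in which the protocol describes them.**
   - Before dosing: a physician's physical and history. Blood pressure is not named. If it is taken, it is a baseline and cannot show that night's drug effect.
   - Equipment (Section V, Measurements and equipment): EEG, EOG, EKG, chin and leg EMG, effort belts, oximetry, microphone, position sensor, pressure catheter in the airway, genioglossus EMG, and mask airflow with CO₂ and, if available, O₂. There is no blood pressure device.
   - Overnight (Section VII, item 6): heart rate, SaO₂ and EEG, with audio and video.
   - Release (Section V): the subject may leave after the recordings if he or she feels alert enough. No reading is required.
   - Afterwards (Section IX): a telephone call at two to three weeks, and review of reported adverse events. Neither is a measurement.

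4. **Listed effects against signals.**
   - Arrhythmia, tachycardia, extrasystoles: EKG and heart rate.
   - Hypertension (item 4): no signal.
   - Hypotension (item 5): no signal.

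5. **Count.** Post-dose blood pressure readings named in the protocol text: 0 per night. Over the 10 planned completers and two nights each, that is 0 readings on 10 × 2 = 20 nights. The count is also 0 for everyone else enrolled (about 13 in Section VI, 15 in Section III).

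**The case against.** The strongest objection is that the record is incomplete. Section IX says the trial will follow an attached Data and Safety Monitoring Plan, which was not available for review. A reader might infer that the trial plans no blood pressure reading at all; the documents do not support that. What Section IX describes of its safety monitoring plan is the review and classification of events, not measurement, so the attachment may not fill the gap, but its content is unknown. This objection stands and limits the finding to the protocol text.

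Four further objections have force:

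- **Doubling.** A reader might infer that the doubled combination raises the risk to blood pressure. Nothing in the documents shows this. Each component is at a strength listed as available alone, the two effects are listed for the single drugs, and neither is among the most common effects given for the combination.
- **Role of the monitoring.** A reader might infer that the protocol claims its monitoring covers every listed effect. It does not. The main argument is the higher single-drug doses, and monitoring is added in support. This is a gap in coverage, not a flat contradiction.
- **Eligibility.** A reader might infer that blood pressure is the only listed toxicity that eligibility addresses. It is not: underlying cardiac disease such as arrhythmia is excluded, and arrhythmia is a listed common effect of pseudoephedrine. That risk is both screened for and monitored. Only well-controlled hypertension is admitted.
- **Limits of a fix.** Readings taken while awake would miss a response during sleep, and the documents give no time course for either drug, so they do not show which times would be most informative.

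It can also be said that a physician is available and could take a reading. That is true, but the protocol does not plan one, and such a reading would depend on a symptom or complaint.

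**Conclusion.** The point holds for the protocol text: it names no blood pressure reading after dosing, while it lists a blood pressure effect for each drug, admits well-controlled hypertension, and relies in part on monitoring limited to heart rate, SaO₂ and EEG. The size is 0 planned post-dose readings on either night, at exactly 2.0 times the marketed combination and 1.0 times the highest single-drug strengths listed.

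This rests on two readings: that the equipment and signal lists are complete as written, and that the physical precedes dosing as the narrative order implies. It also depends on the attached safety plan not scheduling such readings, which could not be checked. It says nothing about whether the dose is acceptable, how likely a blood pressure change is, or the planned efficacy analysis. The change is worth making because it is cheap and closes a specific safety gap.

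**What to change.** Add blood pressure to the measurements in Section V and to the monitored signals in Section VII, item 6. Name a pre-dose reading, for which the existing physical can serve, and at least one post-dose reading before release. Take them while the subject is awake, identically on both nights, and report them by treatment. Because each subject is their own control under blinding, this also gives a within-subject comparison of drug with placebo. If the attached Data and Safety Monitoring Plan already schedules such readings, a citation to it in item 6 is enough.

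In either case, bring Section III, the side-effect lists in Section VII and the monitoring statement in item 6 into line, so that the statement either covers the listed blood pressure effects or says that it does not. The exact timing and any action rule are for the investigators to set.

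The cost is a few minutes per night for staff already present, plus a short change of wording. Awake readings leave the sleep recordings undisturbed but will not capture changes during sleep, and the protocol should say so.
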